## 9.1 ADVERSE EVENTS

AEs will be coded using the Medical Dictionary for Regulatory Activities.

An AE (classified by preferred term) that occurs during the OLTP or thereafter will be considered a treatment-emergent adverse event (TEAE) if it was not present before the date of the first dose of IP in the lead-in study or was present before the first dose of IP in the lead-in study and increased in severity during the OLTP or thereafter. An AE that becomes serious during the OLTP or thereafter will also be considered as TEAE. If more than 1 AE is reported before the date of the first dose of IP in the lead-in study and coded to the same preferred term, the AE with the greatest severity will be used as the benchmark for comparison with the AEs occurring during the OLTP or thereafter that were also coded to that preferred term. An AE that occurs more than 30 days after the date of the last dose of IP will not be counted as a TEAE.

An AE (classified by preferred term) that occurs during the OLTP of the study will be considered a newly emergent adverse event (NEAE) if the AE was not present before the first dose of IP in the OLTP or it was present before the first dose of IP in the OLTP and increased in severity during the OLTP. An AE that becomes serious during the OLTP will also be considered as NEAE. If more than 1 AE is reported before the first dose of IP in the OLTP and coded to the same preferred term, the AE with the greatest severity will be used as the benchmark for comparison with the AEs occurring during the OLTP that were also coded to that preferred term.

An AE (classified by preferred term) that occurs during the DBTP of the study will be considered a newly emergent adverse event (NEAE) if the AE was not present before the first dose of IP in the DBTP or it was present before the first dose of IP in the DBTP and increased in severity during the DBTP. An AE that becomes serious during the DBTP will also be considered as NEAE. If more than 1 AE is reported before the first dose of IP in the DBTP and coded to the same preferred term, the AE with the greatest severity will be used as the benchmark for comparison with the AEs occurring during the DBTP that were also coded to that preferred term.

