An AE (classified by preferred term) that occurs during the SFU of the study will be considered a newly emergent adverse event (NEAE) if the AE was not present before or at Visit 70 or it was present before or at Visit 70 and increased in severity during the SFU. An AE that becomes serious during the SFU will also be considered as NEAE. If more than 1 AE is reported before or at Visit 70 and coded to the same preferred term, the AE with the greatest severity will be used as the benchmark for comparison with the AEs occurring during the SFU that were also coded to that preferred term.

An AE that occurs more than 30 days after the date of the last dose of IP will not be counted as an NEAE.

An SAE that occurred between the date of the first dose of IP in the OLTP and 30 days after the date of the last dose of IP, inclusive, will be considered a treatment-emergent SAE (e.g., TESAE).

The overall number and percentage of patients with TEAEs, NEAEs, death, TESAEs, TEAEs leading to study discontinuation and TEAEs related to study drug during the OLTP will be tabulated overall, and during the DBTP and the SFU by treatment group.

The incidence of common ( $\geq 2\%$  of patients in any treatment group) TEAEs and NEAEs during the OLTP will be summarized overall by preferred term. Similarly, the incidence of common TEAEs and NEAEs during the DBTP and during the SFU will be summarized by preferred term and treatment group and will be sorted by decreasing frequency starting with the weekly rapastinel group followed by the clinically driven schedule rapastinel group.

Listings will be presented for all patients with AEs and patients who died (if any).

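### SAP 9.1 uses Visit 70, the planned end of safety follow-up, as the reference for follow-up NEAEs, so no event starting on the planned follow-up days can count as newly arising

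*SAP*

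**What the plan says.** SAP 9.1 defines newly emergent adverse events (NEAEs) separately for the open-label period (OLTP), the double-blind period (DBTP) and the safety follow-up (SFU). The first two rules refer back to the start of their own period. The double-blind rule, for instance, applies "if the AE was not present before the first dose of IP in the DBTP".

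The follow-up rule differs. An event occurring during the SFU is "considered a newly emergent adverse event (NEAE) if the AE was not present before or at Visit 70", or if it was already present by that visit and worsened during follow-up. There is one further route: "An AE that becomes serious during the SFU will also be considered as NEAE". The severity benchmark uses the same visit: "If more than 1 AE is reported before or at Visit 70 and coded to the same preferred term", the most severe of them is the comparator. An outer limit applies to all NEAEs: "An AE that occurs more than 30 days after the date of the last dose of IP will not be counted as an NEAE".

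The rule feeds planned output. SAP 9.1 tabulates NEAE counts for the SFU by treatment group and also states that "the incidence of common TEAEs and NEAEs during the DBTP and during the SFU will be summarized by preferred term and treatment group".

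The timing comes from other sections. SAP 2.0 starts the SFU once the last scheduled assessment or ET is complete, gives it two weeks, and ends it at the last available assessment. The visit-window table in SAP 14.2 closes the DBTP at Visit 69 (Week 52, Day 364) and places Visit 70 (Week 54, Day 378) within the follow-up.

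**The concern.** A reference point for newly arising events should sit at the start of the period being described. Here it sits at the planned end. Read literally, the new-onset limb excludes the events it was written to capture, and only worsening or becoming serious remains as a route in.

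An event starting between Visit 69/ET and Visit 70 is not picked up elsewhere as an NEAE, because the double-blind rule covers events occurring during the DBTP. The protocol offers no fallback: its section 9.7.6.1 defines NEAEs for the DBTP only.

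The TEAE tables do not replace the missing split. An event is a TEAE "if it was not present before the date of the first dose of IP in the lead-in study", or if it later worsened or became serious. That reference is far earlier, so the follow-up TEAE tables mix events first seen after treatment stopped with preferred terms recurring from the open-label or double-blind periods. Protocol 9.2 gives the follow-up's purpose as monitoring after the product is stopped. A nearly empty NEAE table could be misread as showing that nothing new arose then.

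**Working it through.** **Inputs**

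- Visit 69: Week 52, target Day 364, end of DBTP (SAP 14.2)
- Visit 70: Week 54, target Day 378, within the SFU (SAP 14.2)
- Planned SFU length: 2 weeks; maximum study duration: 70 weeks (SAP 2.0)
- NEAE limit: 30 days after the last dose (SAP 9.1)
- Common-event threshold: 2% of patients in any treatment group (SAP 9.1); planned size 200 per group (SAP 12.0)
- Assumed: Visit 70 falls 14 days after Visit 69/ET, and a completer's last dose is on Day 357 or Day 364

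**1. The plan's own figure.** 16 (OLTP) + 52 (DBTP) + 2 (SFU) = 70 weeks, as stated. In days, 52 × 7 = 364 and 54 × 7 = 378, so the planned SFU has 378 − 364 = 14 days, Days 365 to 378.

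**2. New-onset days.** An onset on day d qualifies only if d is later than the reference visit.

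| Reference | Condition | Qualifying days among 365–378 |
|---|---|---|
| Visit 70, as written | d > 378 | 0 of 14 |
| Visit 69/ET | d > 364 | 14 of 14 |

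All 14 days are inside the 30-day limit, which falls on Day 357 + 30 = 387 or Day 364 + 30 = 394.

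**3. Patients who leave earlier.** Put Visit 69/ET on day T, Visit 70 on T + 14 and the last dose on T − g. With the Visit 69/ET reference, the qualifying days up to Visit 70 number min(14, 30 − g), which is 14 for g up to 16. As written the number is 0 for any g.

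**4. Follow-up running past Visit 70.** Protocol 9.1.3 allows extra safety visits. New-onset days then remain up to the 30-day limit:

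- last dose Day 364: 394 − 378 = 16 days (379–394)
- last dose Day 357: 387 − 378 = 9 days (379–387)

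These days do not make up for the lost ones. If Visit 70 is the final protocol-defined visit, Protocol 9.5.2.1.4 sends later events to the eCRF only when they are serious or judged potentially related to treatment.

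**5. Severity benchmark.** Suppose a patient has a mild event in the DBTP, then a separate moderate event with the same preferred term between Visit 69/ET and Visit 70. Applied literally, the benchmark sentence takes in both events and sets the comparator at moderate. The moderate event does not exceed it, so the rise from mild is not counted.

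**6. Illustration only.** With 200 per group the threshold is 0.02 × 200 = 4 patients. A preferred term newly arising in 4 patients of one arm between Visit 69/ET and Visit 70 would enter the common-NEAE table with the Visit 69/ET reference. As written it would show 0, unless an event worsened or became serious. The documents give no adverse event rates, so the number of patients actually affected cannot be calculated.

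**The case against.** The strongest reply is that little is lost. The SFU NEAE category is an SAP addition, the output is descriptive, and SAP 15.0 limits analyses to what an abbreviated report needs. The affected events can still appear in SFU TEAE counts and the common-TEAE table, in TESAEs if serious, and in the listings. This is right and bounds the severity. It does not rescue the rule: the SAP kept this table after the reduction, and as defined the table cannot show what it is for.

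One could also read the last scheduled assessment in SAP 2.0 as Visit 70, so that the SFU starts there. That conflicts with the mention of ET in the same sentence, with SAP 14.2, and with a two-week SFU inside a 70-week maximum.

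Four narrower points have some force.

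- The benchmark example is not the only reading. The worsening limb taken alone would count a mild DBTP event that becomes moderate in the SFU. The example holds only if the benchmark sentence is applied as worded.
- Parts of both documents are redacted or not shown, so the most that can be said is that no visible section corrects the visit number.
- Days 365–378 describe 52-week completers. Under the sample-size assumptions, with independent relapse and dropout, about (0.81 × 0.80)² = 42% of placebo patients, roughly 84 of 200, get that far. The rest enter follow-up earlier, where step 3 applies. The visible SAP gives no SFU denominator, so the 4-patient case shows the mechanism, not the impact.
- SAP 2.0 ends the DBTP at relapse or discontinuation, while SAP 14.2 ends it at Visit 69. If Visit 69/ET falls later, an event in between could still be unclassified after the visit number is corrected.

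**Conclusion.** The concern holds. On the planned schedule, with Visit 70 taken as 14 days after Visit 69/ET, 0 of 14 follow-up days can produce a new-onset NEAE as written, against 14 of 14 with a Visit 69/ET reference. The result does not depend on whether the last dose is on Day 357 or Day 364. Only an extension past Visit 70 leaves any eligible days: at most 9 or 16 under those two last-dose assumptions, and with narrower eCRF recording.

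The SFU NEAE table need not be completely empty, since worsening and newly serious events still count. The rule is also undefined for a patient with no Visit 70. The damage is confined to one descriptive safety split; TEAE, TESAE and listing coverage remains, and efficacy is untouched. It is a stated rule that gives a wrong table, and it should be corrected.

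**What to change.** In the SFU paragraph of SAP 9.1, replace the Visit 70 reference with Visit 69/ET in all three places: the new-onset limb, the worsening limb and the severity benchmark. Add a sentence that, for patients with no Visit 69/ET assessment, the end date of their last treatment period serves as the reference and as the start of the SFU for this purpose. This covers patients who do not return for final assessments (Protocol 9.3.3). It also brings the SFU rule into line with the start-of-period references used for the OLTP and DBTP.

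In the same edit, state which DBTP end date governs NEAE assignment, so that events between relapse or discontinuation and Visit 69/ET fall in one period or the other.

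The cost is one SAP paragraph and a small change to the derivation code, including the fallback date. No new data are needed.

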### **9.5.2.1 Adverse Events**

An AE is any untoward medical occurrence in a patient or clinical investigation patient administered a pharmaceutical product and which does not necessarily have to have a causal relationship with this treatment. An AE can therefore be any unfavorable and unintended sign (including an abnormal laboratory finding, for example), symptom, or disease temporally associated with the use of a medicinal product, whether or not considered related to the medicinal product (ICH-E2A).

For the purpose of the study center's data collection responsibilities, any untoward event that was reported from the time the patient signed the ICF until 30 days after the final protocol-defined study visit or the last known dose of IP (if the final visit does not occur) is to be considered an AE.

Examples of AEs are as follows:

- Changes in the general condition of the patient
- Subjective symptoms offered by or elicited from the patient
- Objective signs observed by the investigator or other study center personnel
- All diseases that occur after signing informed consent, including any change in severity or frequency of pre-existing disease
- All clinically relevant abnormalities in laboratory values or clinically relevant physical findings that occur during the study schedule

Please note that medical procedures scheduled prior to consenting, but occurring during the study should not be captured as AEs, but should be listed in the medical history if related to a pre-existing condition.

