#### 9.5.2.1.3 *Serious Adverse Events*

An SAE is any untoward medical occurrence that at any dose:

- Results in death
- Is life threatening
- Requires inpatient hospitalization or prolongation of existing hospitalization
- Results in persistent or significant disability/incapacity, or
- Is a congenital anomaly/birth defect

Important medical events that may not result in death, be life threatening, or require hospitalization may be considered serious when, based on appropriate medical judgment, they may jeopardize the patient and may require medical or surgical intervention to prevent one of the outcomes listed in this definition. Examples of such medical events include allergic bronchospasm requiring intensive treatment in an emergency room or at home, blood dyscrasias or convulsions that do not result in patient hospitalization, or the development of IP dependency or drug abuse.

Emergency room visits that do not result in hospitalization should be evaluated for one of the other serious outcomes to determine whether they qualify as SAEs.

Preplanned hospitalizations (eg, elective procedures for pre-existing conditions that did not worsen, such as cosmetic surgery and hysterectomy) are excluded from SAE reporting.

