#### 8.0 EFFICACY ANALYSES

#### 8.1 PRIMARY EFFICACY PARAMETERS

The analysis of the primary efficacy parameter will be performed using the Double-blind mITT Population.

The primary efficacy parameter is the time to first relapse during the 52 weeks of the DBTP, defined as the number of days from the randomization date of DBTP to the relapse date (ie., relapse date – randomization date + 1). Relapse during the DBTP is defined as meeting any of the following criteria:

- Rater-administered MADRS total score  $\geq 18$  at 2 consecutive visits
- $\geq 2$  increase in CGI-S score compared with that obtained at randomization
- Risk of suicide as determined by the investigator
- Need for hospitalization due to worsening of depression as determined by the investigator
- Need for alternative treatment of depressive symptoms as determined by the investigator

Patients who did not meet the above relapse criteria during the 52 weeks of the DBTP, the time to relapse will be censored at the time of completion or discontinuation from the study, or 52 weeks, whichever is earlier.

The primary efficacy analysis will be presented by the cumulative distribution function of time to relapse characterized by the Kaplan-Meier curve for each treatment group.

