## **12.0 DETERMINATION OF SAMPLE SIZE**

The sample size and power calculations are based on the analysis of time to relapse during the first 52 weeks of the DBTP. Assuming a relapse rate of 19% per 26 weeks in the placebo group and a dropout rate of 20% per 26 weeks in all treatment groups, the sample size of 200 per group will have 90% power to detect a hazard ratio of 0.475 for a rapastinel treatment versus placebo at a 0.05 significance level. To achieve this number of randomized patients, approximately 1400 patients need to be enrolled in this study if 50% of patients are qualified for randomization.

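### The double-blind NEAE and TESAE totals by arm can include relapses, so an efficacy difference enters the safety summary, and the visible SAP gives no SAE breakdown by preferred term to separate it

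*SAP*

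**What the plan says.** Protocol 9.5.2.1 gives as an example of an AE "All diseases that occur after signing informed consent, including any change in severity or frequency of pre-existing disease". Protocol 9.5.2.1.3 makes an AE serious if it "Requires inpatient hospitalization or prolongation of existing hospitalization", and the only admissions it leaves out are preplanned ones. One relapse criterion in SAP 8.1 is "Need for hospitalization due to worsening of depression as determined by the investigator".

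SAP 9.1 plans "The overall number and percentage of patients with TEAEs, NEAEs, death, TESAEs, TEAEs leading to study discontinuation and TEAEs related to study drug", overall for the open-label period and by treatment group for the double-blind period (DBTP). The three event classes have different reference points:

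- A **DBTP NEAE** is compared with the state before the first double-blind dose.
- A **TEAE** is compared with the state before the first dose in the lead-in study. An AE that becomes serious from the open-label period onward counts regardless.
- A **TESAE** is any SAE from the first open-label dose to 30 days after the last dose, with no comparison to an earlier state.

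SAP 9.1 also plans a by-arm preferred-term table of TEAEs and NEAEs reaching 2% in any group, and a listing of all patients with AEs. Protocol 9.7.6.1 additionally planned on-therapy SAEs by arm and preferred term. That table does not appear in the visible SAP, whose section 15.0 limits output to what an abbreviated study report needs.

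**The concern.** A relapse is the primary efficacy event and is expected more often on placebo. If relapses are entered as AEs, the placebo safety totals are raised by returning illness. A summary row could then favour rapastinel, or look balanced, while rapastinel causes more events unrelated to depression. This matters most for SAEs. They are few, so a handful of depression admissions can change the comparison, and the visible SAP gives only the by-arm total and a listing.

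**Working it through.** **1. Inputs and the plan's own figure.** SAP 12.0 takes 19% relapse on placebo and 20% dropout in every arm, each per 26 weeks. From these it concludes that "the sample size of 200 per group will have 90% power to detect a hazard ratio of 0.475". The level is 0.05, and protocol 9.7.5 makes tests two-sided. With constant weekly hazards:

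- placebo relapse: −ln(0.81)/26 = 0.00810
- rapastinel relapse: 0.475 × 0.00810 = 0.00385
- dropout: −ln(0.80)/26 = 0.00858

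Observed relapse by 52 weeks is λ/(λ+δ) × [1 − exp(−52(λ+δ))], where λ is the relapse hazard and δ the dropout hazard:

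- placebo: 0.4857 × (1 − 0.4199) = 28.2%, or 56.3 of 200
- each rapastinel arm: 0.3097 × (1 − 0.5239) = 14.7%, or 29.5 of 200

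That is 85.8 events per pairwise comparison. Freedman's formula gives z = √85.8 × 0.525/1.475 = 3.298, and 3.298 − 1.960 = 1.338, so power is 90.9%. The stated 90% is reproduced (Schoenfeld's formula gives 93.2%). The gap in observed relapse is 13.4 points, about 27 patients per 200.

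**2. Which rows a recorded relapse enters.**

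- *NEAE, DBTP:* yes. Patients had just met the stability criteria at the reference point, so the relapse is new or worse.
- *TESAE:* yes if hospitalised, because only the time window matters.
- *TEAE:* yes if hospitalised, through the becomes-serious rule. A non-serious relapse no more severe than at lead-in entry may not qualify, because the depressive episode was already present then. If only events reported as AEs before that dose count as present, it does qualify. The SAP does not say which reading applies.
- *Leading to discontinuation:* not necessarily. Protocol 9.1.2 makes a relapsed patient a completer.

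**3. NEAE total.** Let b be the non-relapse NEAE rate (equal in both arms, independent of relapse), f the share of relapses entered as AEs, and p the relapse proportion. Neither b nor f is in the documents; both are assumed. The total is 1 − (1 − b)(1 − f·p). The rapastinel background that would make the totals equal is 1 − (1 − b)(1 − f·0.2817)/(1 − f·0.1474). At b = 50%:

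| f | placebo v rapastinel total, no true difference | excess hidden by equal totals |
|---|---|---|
| 10% | 51.4% v 50.7% | 0.7 points |
| 25% | 53.5% v 51.8% | 1.7 points |
| 50% | 57.0% v 53.7% | 3.6 points |
| 100% | 64.1% v 57.4% | 7.9 points |

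Over b = 30% to 70% and f = 10% to 100%, the hidden excess runs from 0.4 to 11.0 points.

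**4. TESAE total.** The same formulas apply with the non-relapse SAE rate s in place of b and the hospitalised share of relapses h in place of f, both assumed. At s = 2%:

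| h | placebo v rapastinel total, no true difference | extra patients per 200 hidden by equal totals |
|---|---|---|
| 2% | 2.55% v 2.29% | 0.5 |
| 5% | 3.38% v 2.72% | 1.3 |
| 10% | 4.76% v 3.44% | 2.7 |
| 20% | 7.52% v 4.89% | 5.4 |

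At h = 10%, equal totals would be consistent with non-relapse SAE rates of 2.0% on placebo and 3.3% on rapastinel. Over s = 1% to 3% and h = 2% to 20%, the hidden excess is about 0.5 to 5.5 patients per 200, a 1.1- to 3.7-fold rate.

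**The case against.** A reader might infer that every relapse is a TEAE, and so that the any-TEAE row is inflated by the full relapse difference. The SAP's lead-in reference point does not support that for non-serious relapses. The NEAE row is the one that clearly takes them in.

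A reader might also infer that harm is hidden from anyone using the report. For common non-serious events it is not. If a quarter of relapses were entered under one term, that term would reach about 7% on placebo (0.25 × 28.2%), well above the 2% threshold. A common non-depressive harm would have its own line. Even so, patients can have several AEs, so term counts cannot be subtracted to give the number with any non-relapse event. For SAEs, individual cases can be found in the listing; what is missing is a by-arm tabulation.

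Other rows are less exposed. Protocol 9.5.2.1.1 directs the investigator to answer no on causality when the underlying disease is the likely cause, so the drug-related row should contain few relapses.

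The sizes rest on assumptions. Two relapse criteria are score-based, and nothing readable says whether such relapses also go on the AE page. Recording guidance may sit in redacted text. Equal backgrounds also ignore that placebo relapsers leave earlier: mean double-blind time is 34.8 weeks on placebo against 38.3 on rapastinel. With a constant non-relapse AE hazard that gives 40% on rapastinel, the placebo background is 36.8%. With all relapses entered, the gap is then 6.9 points (57.7% v 50.8%) rather than 8.1. That reduces the effect without removing it.

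Finally, dropping depressive-worsening terms could remove a genuine drug-related worsening. This is a sound reason not to let the reduced version replace the full one.

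**Conclusion.** The point holds for the DBTP NEAE and TESAE totals, and for TEAEs where the relapse is hospitalised. Its TEAE status otherwise depends on a reading that the SAP leaves open. The design inputs put a 13.4-point efficacy difference (28.2% v 14.7%) next to these rows. How much of it enters depends on the shares of relapses entered as AEs and hospitalised, which the documents do not give. Over the assumed ranges the effect runs from negligible to 11.0 points for NEAEs and about 5.5 patients per 200 for TESAEs. The documents do not support a claim that common harms are concealed, or that the discontinuation row must contain relapsers. The firmest gap is the SAE table by arm and preferred term, which the protocol planned and the visible SAP omits. This is an inexpensive improvement to a descriptive safety comparison.

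**What to change.** In SAP 9.1:

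1. Keep the planned all-events totals.
2. Beside them, add DBTP NEAE, TEAE and TESAE rows that exclude relapse-linked depressive-worsening terms. Fix the preferred-term list before unblinding and tie each exclusion to the relapse date on the Relapse CRF. Keep suicidality terms in both versions.
3. Restore the table of SAEs by arm and preferred term from protocol 9.7.6.1.

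Present both versions side by side. Do not replace the all-events totals or rest the tolerability conclusion on the reduced version alone. The discontinuation row need not be duplicated.

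The cost is one extra table block, one restored table, a short term list and a second set of totals to explain. It uses data already collected and changes nothing in patient management or SAE reporting.
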